7.5 SECONDARY ENDPOINT(S)

Absolute number and percentage of patients, who discontinue the initial treatment during study, will be summarized collectively and according to reasons for discontinuation for the dabigatran etexilate and VKA cohort, respectively.

The analysis of secondary endpoints will be based on the patient cohort resulting from the 1:1 matching.

The Morisky questionnaire consists of 8 question and will be answered at the 6- months visit. Each question can be scored with 0 or 1. For questions 1-7, 'no' will be scored with 0 and 'yes' with 1. For question 8, 'None/rarely' will be scored with 0 and all other answers with 1. The Morisky score is given by the sum of the values of each question, which implies a score between 0 and 8.

The categorisation of patients into low adherence (score >2), medium adherence (score=1,2) and high adherence (score=0) is done according to Morisky. The score will only be calculated for patients who answered all eight questions. In case that the proportion of the patients who did not answers all questions is too high (i.e. >20%) a sensitivity analysis will be conducted in which the score will be calculated if up to 2 questions per patient are missing. Patients who changed their initial treatment or withdrew from the study before the 6-months visit, will be displayed seperately from those for which the Morisky score could not be calculated for other reasons. Patients with missing data will be analyzed regarding to their baseline characteristics in comparision to the patients with an evaluable Morisky score; patients with missing values at the 6-months visit will be stratified into (i) the groups of study drop-outs, (ii) treatment drop-outs and (iii) patients with missing values because of other reason. The last mentioned analyses will only be done for strata of at least 200 patient (overall and for each treatment group).

Number and percentage of patients within the different adherence classes will be displayed for dabigatran etexilate and VKA patients, respectively. Furthermore the following subgroups will be presented for adherence (overall and for each treatment group):

- CHA₂DS₂-VASc-Score (<2, ≥2)
- Age (<65, 65- <75, ≥75)
- Previous stroke Yes, No)
- Medical specialty of attending physician (Internist, Cardiologist, General practitioner, Other)
- Daily dose of Pradaxa® at initial visit (2x110mg daily, 2x150mg daily) [Patients treated with Pradaxa® only]
- HAS-BLED-Score (<3, ≥3).

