2.2 Study objectives

The objective of this open, prospective, controlled, multicentre, non-interventional cohort study (NIS) is to record the treatment compliance (measured as persistence and adherence) of patients treated with dabigatran etexilate or VKA.

Primary study objective:

- To compare persistence in patients treated with dabigatran etexilate or VKA.

Secondary study objectives:

- To compare adherence in patients treated with dabigatran etexilate or VKA
- To record the reasons for any treatment discontinuation

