Reasons for change 2:

After 6 months of site and patient recruitment it became evident that the targeted patient and site numbers will not be met and that recruitment time should be longer.

Therefore the planned patient number will be reduced to 1600 and site number to 800.

Recruitment time will be prolonged to 16 months (LPI December 2015), thus study duration will also increase. LPO is now planned for December 2016.

Other timelines will change accordingly.

CHANGE 3: ADAPT TIME SCHEDULE, SITE NUMBERS AND PATIENT NUMBERS

Section of the protocol: Statistics Section Determination of number of patients

It is planned to include a total of 4000 patients in this non-interventional, controlled, observational study (dabigatran etexilate: 2000 patients, VKA: 2000 patients).

Calculation of statistical power:

All analyses are purely exploratory by virtue of the non-interventional study design. On the following assumptions:

- 15% drop-outs /missing values after one year,
- 2000 dabigatran etexilate patients, 2000 VKA patients, with 66% of VKA patients with a matching partner in the dabigatran etexilate group (i.e. total number of patients in the 1:1 matched analysis is 2640)
- a persistence rate of 63% in the dabigatran etexilate group (cf. 1-year persistence with a 60-day permissible medication gap as reported by Zalesak ¹⁹)).

the power for a descriptive p value ≤ 0.05 in a 2-tailed test for the same persistence rates is as follows (dependent on the VKA persistence rate):

Assumed VKA persistence rate*	51%	53.8%	56.5%
Power	100%	99.7%	91.7%

* The calculations were performed with ADDPLAN6 and are based on survival time analysis test statistics and the endpoint variables "Time to permanent treatment discontinuation".

Was changed to:

It is planned to include a total of 1600 patients in this non-interventional, controlled, observational study (dabigatran etexilate: 800 patients, VKA: 800 patients).

Calculation of statistical power:

All analyses are purely exploratory by virtue of the non-interventional study design. On the following assumptions:

- 15% drop-outs /missing values after one year,
- 800 dabigatran etexilate patients, 800 VKA patients, with 66% of VKA patients with a matching partner in the dabigatran etexilate group (i.e. total number of patients in the 1:1 matched analysis is 1056)
- a persistence rate of 63% in the dabigatran etexilate group (cf. 1-year persistence with a 60-day permissible medication gap as reported by Zalesak (¹⁹)).

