7.4 PRIMARY ENDPOINT(S)

The analysis of the primary endpoint will be based on the patient cohort resulting from the 1:1 matching. Time until termination of treatment will be presented for both treatment groups (Dabigatran etexilate vs. VKA) by Kaplan-Meier estimates and displayed graphically, respectively. Especially for time points 3, 6, 9 and 12 months Kaplan-Meier estimates for persistence will be calculated.

The comparison of persistence between the treatments with dabigatran etexilate versus VKA will be conducted by means of the stratified Log-rank test, which takes dependencies resulting from the matching of the treatment groups into account. Patients who discontinue

study prematurely and without documented treatment discontinuation will be censored at study termination. Patients completing the study as planned will be censored at the day after last visit, if no earlier treatment discontinuation is documented. Association between patient characteristics (incl. method of treatment) and persistence will be determined by means of cox regression (univariate and multivariate model). First, univariate regression for each of the independent variables will be performed. Afterwards, all covariates will be entered into a stepwise multivariate regression. The entry level will be $p=0.5$ and the stay level $p=0.1$. Baseline characteristics will be presented stratified by patients who discontinued the study prematurely versus no discontinuation.

A multivariate Cox Regression model (including factors for the calculation of the propensity score and the choice of treatment) will be used as sensitivity analysis. All patients, who are within the “common support” of the empiric PS density function (instead of the matched pairs), will be included in this analysis. The “common support” will be determined after patients with a propensity score above the 97.5% percentile and below the 2.5% percentile have been excluded for each treatment group, respectively. This will be done to avoid high influence of patients with extreme PS.

The following covariates will be used –depending on the sample size- for the Propensity Score Matching and the sensitivity analysis

- CHA₂DS₂-VASC Score (<2, ≥ 2)
- HAS BLED-Score (<3, ≥ 3)
- Age at registration (<65, 65-<75, ≥ 75)
- Previous stroke (Yes, No)
- Treatment (VKA, Pradaxa[®]) (sensitivity analysis only)

and the following covariates will be used –depending on the sample size- for the Cox regression

- CHA₂DS₂-VASC Score (<2, ≥ 2)

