- HAS BLED-Score (<3, ≥ 3)
- Age at registration (<65, 65-<75, ≥ 75)
- Previous stroke (Yes, No)
- Medical specialty of attending physician (Internist, Cardiologist, General practitioner, Other)
- Treatment (VKA, Pradaxa[®]).

Additionally, the following subgroups will be presented for persistence (overall and for each treatment group):

- CHA₂DS₂-VASC-Score (<2, ≥ 2)
- Age (<65, 65- <75, ≥ 75)
- Previous stroke (Yes, No)
- Medical specialty of attending physician (Internist, Cardiologist, General practitioner, Other)
- Daily dose of Pradaxa[®] at initial visit (2x110mg daily, 2x150mg daily) [Patients treated with Pradaxa[®] only]
- HAS-BLED-Score (<3, ≥ 3).

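### The discontinuation-reasons table and the dabigatran dose subgroups are limited to the matched cohort although neither needs a matched partner: at the planned 66% match rate, 272 of 800 dabigatran patients and about 186 to 234 documented stops fall outside them

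*SAP*

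**What the plan says.** SAP 7.4 opens with "The analysis of the primary endpoint will be based on the patient cohort resulting from the 1:1 matching". Under that statement it lists the univariate and stepwise Cox models and the persistence subgroups without naming another analysis set. One subgroup is "Daily dose of Pradaxa[®] at initial visit (2x110mg daily, 2x150mg daily) [Patients treated with Pradaxa[®] only". SAP 7.5 covers the reasons for discontinuation, Morisky adherence and the same dose subgroup for adherence, and says "The analysis of secondary endpoints will be based on the patient cohort resulting from the 1:1 matching". Table 6.3:1 agrees: primary and secondary endpoints are marked for the matched group only. The Full Analysis Set (FAS) is defined in SAP 6.3 but has no column in that table. Protocol 7.3 likewise puts persistence and reasons for discontinuation on the matched cohort.

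The objectives are worded differently for the different outcomes. Protocol 2.2 sets out to compare persistence and adherence, but for reasons the aim is "To record the reasons for any treatment discontinuation".

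Three outputs are planned on a wider set:
- the sensitivity Cox model (propensity-score factors plus treatment), in all patients within the common support (SAP 7.4);
- initial dose and dose changes, with the changes described for the Treated Set (SAP 7.7);
- adverse events leading to discontinuation (SAP 7.8), with safety endpoints on the Treated Set in Table 6.3:1.

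**The concern.** Protocol 7.1 and 7.3 introduce matching so that the two drug groups can be validly compared. A tally of reasons for stopping within each drug is not in itself such a comparison. A split by dabigatran dose has no VKA side at all. Dropping a dabigatran patient from these outputs because no VKA patient has a similar propensity score removes information and yields no gain in validity.

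The cost is incomplete reporting of reasons and wider intervals for the dose groups. It also sits awkwardly with protocol 3.2, which presents the sample as representative of treated patients. Local Amendment 2 extended recruitment by a year to move from 1050 to 1600 patients, a gain of 550. The restriction is then expected to leave 544 patients out of the reasons table.

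**Working it through.** **Inputs** (Local Amendment 1, Change 3, the current sample-size text)
- Size: "It is planned to include a total of 1600 patients", 800 per drug.
- Match rate: "with 66% of VKA patients with a matching partner in the dabigatran etexilate group".
- Dabigatran: "a persistence rate of 63% in the dabigatran etexilate group", so 37% stop by 12 months.
- VKA persistence 51%, 53.8% or 56.5%, so 49%, 46.2% or 43.5% stop.
- Drop-out 15% at one year.

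**The plan's own figure.** 2 × 800 × 0.66 = 1056, which agrees with "total number of patients in the 1:1 matched analysis is 1056". That is 528 pairs, leaving 800 − 528 = 272 unmatched per drug, or 34% (544 in total).

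**Stops outside the matched cohort.** The same stop rates are assumed for matched and unmatched patients. The plan does not say how drop-out overlaps with stopping, so three treatments are shown:
- No drop-out: 272 × (0.37 + 0.49) = 234 and 272 × (0.37 + 0.435) = 219.
- Stops reduced by 15%: 0.85 × 234 = 199 and 0.85 × 219 = 186.
- Exponential competing drop-out: the documented fraction is l/(l+c) × (1 − exp(−(l+c))), with l = −ln(persistence) and c = −ln(0.85). For dabigatran it is 0.344. For VKA it is 0.456 at 51% and 0.405 at 56.5%. This gives 272 × (0.344 + 0.456) = 218 and 272 × (0.344 + 0.405) = 204. The corresponding totals are 599 to 640 stops in all 1600 patients and 395 to 422 in the 1056 matched.

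Across the three treatments and the VKA rates, the range is 186 to 234.

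**Dependence on the match rate**

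| Matched | Unmatched per drug | Stops outside matched cohort |
|---|---|---|
| 50% | 400 | 274–344 |
| 66% (plan) | 272 | 186–234 |
| 80% | 160 | 109–138 |
| 90% | 80 | 55–69 |

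**Precision of the dose subgroups.** The documents do not give the dose split. If half of the dabigatran patients were on each dose (an assumption), the 95% half-width for 63% persistence is 1.96 × √(0.63 × 0.37 / 264) = 5.8 points on matched patients and 1.96 × √(0.63 × 0.37 / 400) = 4.7 points on all. With 30% of patients in a dose group the figures are 7.5 and 6.1; with 70%, 4.9 and 4.0. For adherence the numbers are smaller, because patients off the initial drug at six months have no score.

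**Cox models.** Moving the univariate and stepwise models from 1056 to 1600 patients would multiply standard errors by about √(1056/1600) = 0.81, a 19% reduction. The sensitivity model does not have this deficit. After 2.5%/97.5% trimming it keeps at most 0.95 × 800 = 760 per drug (1520), before the overlap restriction. At that upper bound its standard errors are only √(1600/1520) = 1.026 times those on all 1600.

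**The case against.** The case for leaving the plan alone has four parts.

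1. **Patient factors.** A reader might infer that all results on factors linked to persistence are confined to the matched cohort. They are not. The common-support model covers CHA₂DS₂-VASc, HAS-BLED, age, previous stroke and treatment. Only physician specialty has no model outside the matched pairs. This part of the objection stands, and the 19% applies only to the univariate and stepwise models.

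2. **Reasons for stopping.** A reader might infer that the objective of recording reasons goes unmet for a third of stops. The documents do not support that. Reasons are collected for every patient at visits 2 to 5, and adverse events leading to discontinuation are tabulated in the safety analysis. Protocol 5.2.2.1 even counts lack of efficacy as an adverse event. This largely stands: what is lost is a complete table of reasons, mainly the non-adverse-event ones.

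3. **Selectivity.** A reader might infer that the unmatched patients are those least like the other drug group, so that the restricted tables are biased. This is possible but not shown. The propensity model has four coarse factors and so at most 2 × 2 × 3 × 2 = 24 distinct scores. Many unmatched patients may simply be surplus within a score that also contains matched pairs. The calculation above applies equal stop rates and says nothing about bias.

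4. **Matched display is defensible.** Reasons are shown side by side by drug, and all analyses are descriptive. An unmatched display invites an unadjusted comparison. This supports keeping the matched reasons table, but not omitting the complete one. It does not touch the dose subgroups, which have no comparator drug.

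**Conclusion.** The concern holds for two outputs: the reasons-for-discontinuation table, and the dabigatran-only dose subgroups for persistence and adherence. At the planning match rate, 272 of 800 dabigatran patients are outside the persistence dose subgroups and about 186 to 234 documented stops (34%) are outside the reasons table.

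These are expectations, not counts. They rest on the 66% match rate, the planning persistence rates, 15% drop-out, and equal stop rates in matched and unmatched patients. The 66% need not be what the four-factor propensity model in the SAP delivers. At 90% matched the loss falls to 80 patients and about 55 to 69 stops.

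The consequence is modest: an incomplete table, mainly for reasons unrelated to adverse events, and roughly one percentage point of half-width in a dose group of half the dabigatran patients. The patient-factor models are only partly affected, and the matched primary comparison not at all. This is a nearly free improvement, not a flaw in the main result.

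**What to change.** - In Table 6.3:1 and SAP 7.4/7.5, present the number and reasons of discontinuation per drug, and the dabigatran dose subgroups for persistence and adherence, in all eligible patients. Use the protocol 7.3 definition (documented, at least one prescription, main diagnosis non-valvular atrial fibrillation). The SAP's FAS is narrower because it also requires an evaluable efficacy endpoint. State whether the SAP 6.2 exclusions apply as well.
- Keep the matched version of the reasons table for any reading of one drug against the other.
- Optionally, run the univariate and stepwise Cox models on all eligible patients too, so that physician specialty is also examined outside the matched pairs.
- If a Kaplan-Meier estimate per drug is added in all eligible patients, label it descriptive and unadjusted.
- Leave the matched primary comparison as it is.

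The cost is a few lines of SAP text and the same programs run on a larger set. No new data are needed.

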The analysis is performed on the basis of the patient cohorts resulting from the 1:1 matching. Kaplan Meier estimates for the time to discontinuation of treatment (cf. definition in section 5.1.) will be calculated separately for the dabigatran and the VKA patient group and illustrated graphically. In particular, the Kaplan Meier estimates for persistence at time 3, 6, 9 and 12 months will be reported. The comparison in terms of the persistence of patients on treatment with dabigatran versus VKA will be performed by means of the stratified log-rank test, which takes account of the dependency of treatment groups resulting from matching (cf. Klein, Moeschberger, 1997, ²²). Patients who discontinued the study prematurely and for whom no treatment discontinuation is documented will be censored at the time of study discontinuation. Patients who end the study as planned will be censored on the day after the last visit if no previous treatment discontinuation is documented.

The absolute number and proportion of patients discontinuing the initial treatment in the course of the study will be summarised overall and according to the reasons for discontinuation for the dabigatran and VKA cohorts.

The association of patient characteristics (including treatment allocation) with persistence will be investigated by means of Cox regression models (univariate and multivariate models). Baseline characteristics will be presented stratified for patients who discontinue the treatment in the course of the study and those who do not.

A multivariable Cox regression model (including the factors used for calculating the PS and choice of treatment) will be reported as a sensitivity analysis. For this analysis, all patients who are within the common supports of the empirical density function of the PS (instead of matched pairs) will be included; the common support is determined after excluding patients with a propensity score above the 97.5% percentile and below the 2.5% percentile in each treatment group in order to avoid a strong influence from patients with extreme PS values.

Adherence

The analysis is performed on the basis of the patient cohort resulting from 1:1 matching. The Morisky questionnaire consists of 8 questions and will be presented at the time of the 6-month visit. The analysis and categorisation of patients into the categories

- poor adherence (score >2)
- medium adherence (score=1, 2) and
- high adherence (score=0)

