Attachment 1: Morisky questionnaire

NIS 1160.xxx:

**Drug persistence/adherence in patients being treated with
Pradaxa® (dabigatran etexilate) or vitamin K antagonists (VKA)
for stroke prevention
in non-valvular atrial fibrillation (AF)**

Site number: _____

Patient number: _____

Visit 3, date: _____

Dear patient,

You have said that you are taking medicine for stroke prevention in atrial fibrillation.

Some patients have experienced various problems associated with their medication-taking behaviour and we are interested to find out about your experiences.

There are no right or wrong answers.

Please answer each question on the basis of your personal experience with your medicine for stroke prevention in atrial fibrillation.

Please tick the answer that applies		No	Yes
1.	Do you sometimes forget to take your stroke prevention tablets?		
2.	People sometimes miss taking their medicines for reasons other than forgetting. Thinking over the past 2 weeks, were there any days when you did not take your medicine for stroke prevention?		
3.	Have you ever cut back or stopped taking your medicine without telling your doctor because you felt worse when you took it?		
4.	When you travel or leave home, do you sometimes forget to bring along your medicine for stroke prevention?		
5.	Did you take your medicines for stroke prevention yesterday?		
6.	When you feel like your stroke prevention is under control, do you sometimes stop taking your medicine?		
7.	Taking medicine every day is a real inconvenience for some people. Do you ever feel hassled about sticking to your treatment plan?		
Please tick the answer that applies		Never/rarely	Once in a while
1.	How often do you have difficulty remembering to take all your medicine?		
		Sometimes	Usually
		All the time	

© Morisky Medication Adherence Scale (MMAS-8-item) German

BI No.: 1160.218

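### SAP 7.5 scores item 5 of the Morisky questionnaire in the wrong direction, so a fully adherent patient scores 1 and cannot be classed as high adherence

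*SAP*

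**What the plan says.** The adherence category at the 6-month visit is the first secondary endpoint in Protocol 5.1.1 and SAP 5.2, and comparing adherence between the cohorts is a stated objective in Protocol 2.2.

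SAP 7.5 is the only place with item-level scoring:

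- Items 1 to 7: "For questions 1-7, 'no' will be scored with 0 and 'yes' with 1".
- Item 8: "For question 8, 'None/rarely' will be scored with 0 and all other answers with 1".
- Total: "The Morisky score is given by the sum of the values of each question, which implies a score between 0 and 8".
- Categories: "The categorisation of patients into low adherence (score >2), medium adherence (score=1,2) and high adherence (score=0) is done according to Morisky".
- Completeness: "The score will only be calculated for patients who answered all eight questions". If more than 20% of patients have incomplete questionnaires, a sensitivity analysis also scores those with up to two missing items.

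Protocol 7.3 uses the same cut-offs and also refers to Morisky for the categorisation, but it does not say how each item is scored. SAP section 4 declares no changes to the planned analysis.

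The questionnaire is in Protocol Attachment 1. Item 1 is typical of most items: "Do you sometimes forget to take your stroke prevention tablets". Item 5 reads: "Did you take your medicines for stroke prevention yesterday".

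**The concern.** The total is a count of problems, so each item has to contribute a point for the non-adherent answer. On items 1 to 4, 6 and 7, yes is the non-adherent answer (forgetting, missing days, cutting back, leaving the medicine behind, stopping when things seem under control, feeling hassled). On item 5, yes means that the medicine was taken. The SAP rule therefore charges a point for adherence on item 5 and gives credit for a missed dose.

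Because high adherence is reserved for a total of 0, this is more than a small shift. The category meant for the best-adhering patients is closed to all of them who complete the questionnaire. The overall distribution, the comparison of dabigatran with VKA and the six adherence subgroup presentations in SAP 7.5 all use the same score.

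**Working it through.** **Inputs.** The scoring rule and cut-offs come from SAP 7.5, and the item wording from Protocol Attachment 1. Let K be the number of non-adherent answers on the seven items other than item 5 (0 to 7).

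**The two scores.**

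- Correct score = K + 0 if item 5 is yes; K + 1 if item 5 is no.
- SAP score = K + 1 if item 5 is yes; K + 0 if item 5 is no.

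So SAP score = correct score + 1 for yes on item 5, and correct score − 1 for no. Every complete questionnaire is off by exactly one point.

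**The SAP's stated range.** The SAP rule gives 0 to 8, as stated. The correct rule also gives 0 to 8, so a range check would not reveal the error.

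**Extreme patients.**

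- Adherent on every item: 0+0+0+0+1+0+0+0 = 1, medium (correct: 0, high).
- Non-adherent on every item: 1+1+1+1+0+1+1+1 = 7 (correct: 8; both low).

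**Category changes by K.**

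| K | Item 5 yes: correct → SAP | Item 5 no: correct → SAP |
|---|---|---|
| 0 | 0 → 1, high → medium | 1 → 0, medium → high |
| 1 | 1 → 2, stays medium | 2 → 1, stays medium |
| 2 | 2 → 3, medium → low | 3 → 2, low → medium |
| 3 or more | stays low | stays low |

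The category is wrong when K = 0 or K = 2. There is 1 pattern with K = 0 and C(7,2) = 21 patterns with K = 2, each with two possible answers to item 5: 2 × (1 + 21) = 44 of 2⁸ = 256 patterns. Full enumeration gives the same: 1 high to medium, 21 medium to low, 1 medium to high, 21 low to medium.

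Exactly one complete pattern is classed as high under the SAP: K = 0 with no on item 5. That patient denies forgetting (item 1) and denies any day without the medicine in the past two weeks (item 2), yet says it was not taken yesterday. These answers are close to contradictory.

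**How many patients this could affect (assumption).** The documents give no item response rates. Suppose items are independent, each of the other seven has probability q of a non-adherent answer, and item 5 is answered yes with probability a.

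- Correct proportion high = (1−q)⁷ × a
- SAP proportion high = (1−q)⁷ × (1−a)
- Proportion in the wrong category = (1−q)⁷ + 21q²(1−q)⁵, whatever the value of a

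For q = 0.05: 0.95⁷ = 0.698 and 21 × 0.0025 × 0.95⁵ = 0.041, sum 0.739.

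| q | High, correct (a = 0.90 to 0.99) | High, SAP (a = 0.90 to 0.99) | Wrong category |
|---|---|---|---|
| 0.02 | 78.1% to 85.9% | 8.7% to 0.9% | 87.6% |
| 0.05 | 62.9% to 69.1% | 7.0% to 0.7% | 73.9% |
| 0.10 | 43.0% to 47.4% | 4.8% to 0.5% | 60.2% |
| 0.20 | 18.9% to 20.8% | 2.1% to 0.2% | 48.5% |

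**Between cohorts.** The SAP's proportion high falls as a rises, while the correct proportion rises. With q = 0.05 in both cohorts, one with a = 0.99 truly has more high adherers than one with a = 0.90 (69.1% against 62.9%). The SAP would report 0.7% against 7.0%, which reverses the order.

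**The case against.** The strongest reply is that both documents invoke Morisky, so a programmer who knows the instrument might reverse item 5 anyway. That makes literal programming a risk rather than a certainty, but it does not cure the plan. The reference to Morisky is attached to the categories, whereas the item-level sentence is explicit and makes no exception for item 5.

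Several limits on the scope do stand:

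- The fault lies in a derivation rule, not in data collection. Completed questionnaires are entered in the database (Protocol 8.2 and 8.3), so the score can be rebuilt from the item answers.
- A one-point error in every score is not a category error in every patient. The 44 of 256 counts patterns, not people, and the percentages above rest on assumed response rates.
- The same rule applies to both cohorts. The direction and size of any bias between them cannot be known in advance; cancellation is possible but not assured.
- The statement that no adherent patient can be classed as high holds for complete questionnaires. In the conditional sensitivity analysis, an adherent patient who leaves item 5 blank could total 0, because no rescaling is specified.
- The endpoint is secondary, and all analyses are descriptive. Persistence and reasons for discontinuation are untouched. Even so, a descriptive percentage has to describe what its label says.

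**Conclusion.** The concern holds: the scoring rule is wrong as written and must be corrected. That conclusion needs only the SAP rule and the questionnaire wording; it requires no outside source and no assumption about response rates. If the rule is followed, the adherence endpoint is not valid: every complete score is off by one, and high adherence can be reached only by a patient reporting that yesterday's medicine was not taken. The share of patients misclassified, roughly half to almost nine in ten, is illustrative and depends on independent items with 2% to 20% non-adherent answers on each of the other seven. The damage is confined to the adherence endpoint and its subgroup tables, and it is fully repairable before analysis.

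**What to change.** Replace the item-scoring sentences in SAP 7.5 with:

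> Items 1 to 4, 6 and 7: no = 0, yes = 1. Item 5: yes = 0, no = 1. Item 8: Never/rarely = 0, any other answer = 1.

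State that the same coding applies in the sensitivity analysis for incomplete questionnaires. The item 8 wording also brings the SAP's answer label into line with Attachment 1.

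Add two test cases to the programming check: the pattern that is adherent on every item must total 0, and the pattern that is non-adherent on every item must total 8. Under the present rule they total 1 and 7, so the test catches what the range check misses.

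The cost is one SAP amendment entry and one line of code. No new data are needed, and the cut-offs stay as they are.
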